17.1 Sample size

For each treatment arm, the optimal Bryant-Day 2-stage design (ref: J. Bryant and R. Day. Incorporating toxicity considerations into the design of two-stage phase II clinical trials. *Biometrics*. 2000: 51(4):1372-1383) will be applied with a modification. This design shields patients from an ineffective or toxic treatment by requiring early termination of the trial if after induction cycle I either the CR rate is poor or the severe toxicity rate is high. In this trial, severe toxicity has been defined as any side effect or infection of CTCAE grade 4 during induction cycle I. The following parameters and decision rules are used:

- P_{CR0} is the largest CR probability which, if true, implies that the therapeutic activity is too low and does not warrant further investigation of the regimen. In the present trial, P_{CR0} has been taken as 20%.
- P_{CR1} is the lowest CR probability which, if true, implies that the therapeutic activity is sufficiently high and does warrant further investigation of the regimen. In the present trial, P_{CR1} has been taken as 40%.
- P_{tox0} is the smallest severe toxicity occurrence probability which, if true, implies that the therapeutic toxicity is unacceptable and does not warrant further investigation of the regimen.
 In the present trial, P_{tox0} has been taken as 40%.
- P_{tox1} is the largest severe toxicity occurrence probability which, if true, implies that the therapeutic toxicity is acceptable and does warrant further investigation of the regimen. In the present trial, P_{tox1} has been taken as 20%.

Statistical errors will be:

- α_{CR} is the accepted probability of recommending for further investigation a regimen with a true CR rate equal to or lower than P_{CR0}. In the present trial, α_{CR} has been taken as 0.10.
- α_{tox} is the accepted probability of recommending for further investigation a regimen with a true severe toxicity rate equal to or higher than P_{tox0}. In the present trial, α_{tox} has been taken as 0.10.

- β is the accepted probability of rejecting from further trials a regimen with a true CR rate at least equal to P_{CR1} and a true toxicity rate equal to or lower than P_{tox1}. In the present trial, β has been taken as 0.10.

These design parameters imply that in each treatment arm a maximum of 54 patients who started with induction cycle I will be assessed after induction cycle I for CR rate and severe toxicity, with an interim analysis after the first 24 patients, or as soon as 9 severe toxicities have been reported in the first 24 registered patients, whichever comes first:

- if after the first 24 patients in a treatment arm ≤ 5 CR's (20.8%) are observed, or if ≥ 9 severe toxicities (37.5%) are observed, that arm will be closed to further patient entry with the conclusion that the arm is not enough active or is too toxic, and should not be further investigated. Otherwise patient entry will be extended to 54 patients. However, when 24 patients have been randomized to each treatment arm, a maximum of 4 more patients may be randomized to each treatment arm before the randomization will be put on hold while awaiting the data for and results of the interim analysis.
- If after 54 patients in a treatment arm ≤ 14 CR's (14/54 = 25.9%, 95% CI = 15.0-39.7%) are observed, or if ≥ 18 severe toxicities (18/54 = 33.3%, 95% CI = 21.1-47.5%) are observed, the conclusion will be that the arm is not enough active or is too toxic, and should not be further investigated.
- Otherwise, the trial will conclude that the arm is active and feasible, and warrants further investigation in this patient population.

Since this design applies per treatment arm and does not take into account that the dose in arm B is higher than the dose in arm A, which implies that the true probability of severe toxicity in arm B is not smaller than in arm A and also that the true CR rate in arm B is not smaller than arm A, unless the latter could be explained by a high toxicity rate in arm B, the above stopping rules will be modified in the following way:

- if the observed toxicity rate in arm B is lower than in arm A, the average toxicity rate of both treatment arms will be used in the stopping/decision rules in both arms.
- If the observed CR rate in arm B is lower than in arm A, and this cannot be explained by a high toxicity rate in arm B, the average CR rate of both treatment arms will be used in the stopping/decision rules in both arms.

Before the interim analysis, CR and toxicity data on induction cycle I will be actively requested for on a monthly basis. For this purpose a short questionnaire will be generated, which should be completed as soon as cycle I has been evaluated, or as soon as it has been decided that cycle I will not be administered at all. In order to overcome dropouts due to ineligibility, 120 patients will be randomized. With an expected accrual rate of 60 patients per year, entry will be completed in about 2-2.5 years, depending on the speed of initiation in each country.

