12.1 Alemtuzumab

The most frequent adverse events are acute infusion related toxicity including rigors, fever, nausea and vomiting, hypotension, fatigue, rash, urticaria, dyspnoea, headache, pruritus and

diarrhea. The majority of these adverse events are mild to moderate in severity. According to the data in CLL patients the infusion related events decrease in incidence during the treatment, most striking after the first week of therapy. The most serious toxicity of alemtuzumab is infections. The reported opportunistic infections of grade 3 or 4 during the phase II studies are given in table 1. Most frequent infections reported are herpes simplex and pneumonia caused by *Pneumocystis carinii,* cytomegalovirus, *Aspergillus* and Herpes zoster. Mucormycosis infection is also reported but is uncommon.

Infection-site	Infections	
Pathogen	No	% of patients
Pneumonia	23	15.4
Bacterial	8	5.4
PCP	5	3.4
Fungal	4	2.7
Interstitial	2	1.3
Other	5	3.4
Sepsis/bacteremia	15	10.1
Line infection	8	5.4
Sepsis	7	4.7
Herpes infection	7	4.7
CMV	4	2.7
Herpes simplex	1	0.7
Herpes zoster	2	1.3

Table 1. Infections grade 3 or 4 reported during the phase II trials

Hematological toxicity is common but not too relevant for this study. Transient decrease in hemoglobin was observed during therapy. All patients developed lymphopenia. The total number of T-cells was intensively reduced. By the end of therapy T-cell recovery started to occur, regardless of the total cumulative dose of alemtuzumab given.

In phase II studies adverse events contributing to discontinuation of treatment were reported in 19-29% of CLL patients.

13 Reporting serious adverse events

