13.1 Definitions

Adverse event (AE)

An adverse event (AE) is any untoward medical occurrence in a patient or clinical study subject during protocol treatment. An AE does not necessarily have a causal relationship with the treatment. An AE can therefore be any unfavorable and unintended sign (including an abnormal laboratory finding), symptom, or disease temporally associated with the use of a medicinal (investigational) product, whether or not related to the medicinal (investigational) product.

Adverse reaction (AR)

Adverse reactions (AR) are those AEs of which a reasonable causal relationship to any dose administered of the investigational medicinal product and the event is suspected.

Serious adverse event (SAE)

A serious adverse event is defined as any untoward medical occurrence that at any dose results in:

- death
- a life-threatening event (i.e. the patient was at immediate risk of death at the time the reaction was observed)
- hospitalization or prolongation of hospitalization
- significant / persistent disability
- a congenital anomaly / birth defect
- any other medically important condition (i.e. important adverse reactions that are not immediately life threatening or do not result in death or hospitalization but may jeopardize the patient or may require intervention to prevent one of the other outcomes listed above)

Note that ANY death, whether due to side effects of the treatment or due to progressive disease or due to other causes is considered as a serious adverse event.

Unexpected SAE

Unexpected Serious Adverse Events are those SAE's of which the nature or severity is not consistent with information in the relevant source documents. For a medicinal product not yet approved for marketing in a country, a company's Investigator's Brochure will serve as a source document in that country.

Suspected unexpected serious adverse reaction (SUSAR)

All suspected ARs which occur in the trial and that are both unexpected and serious.

Protocol treatment period

The protocol treatment period is defined as the period from the first study-related procedure until 30 days following the last dose of protocol treatment or until the start of another systemic anticancer treatment off protocol, if earlier.

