17.2 Analyses

All randomized patients, eligible and who started the induction treatment will be included in the analysis, according to the intention to treat.

Those patients who are not in CR within 2 weeks after induction cycle I will be considered as treatment failures.

The estimated CR rate after induction cycles 1 and 2 along with the 95% CI interval will be presented for each treatment arm.

The estimated severe toxicity rate (i.e. any side effect or infection of CTCAE grade 4) along with the 95% CI interval will be presented for each treatment arm.

The actuarial curves for EFS, DFS and OS will be computed using the Kaplan-Meier method and 95% CIs will be constructed.

Actuarial probabilities of relapse after CR or death in CR with corresponding standard errors will be calculated using the competing risk method.

In addition the analysis of toxicity will be done tabulation of the incidence of side effects and infections with CTCAE grade 2 or more (appendix D).

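### The severe-toxicity count has no exemption for expected haematological grade 4, so the stopping rule can close an arm for an effect the protocol itself sets aside

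*Protocol*

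**What the plan says.** Section 14.1 makes the percentage of patients with severe toxicity in cycle I a primary endpoint in each arm. Section 17.1 defines the event: "severe toxicity has been defined as any side effect or infection of CTCAE grade 4 during induction cycle I". Section 17.2 repeats the definition for the final estimate: "The estimated severe toxicity rate (i.e. any side effect or infection of CTCAE grade 4". Neither mentions haematological events.

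This count is compared with an acceptable rate of 20% and an unacceptable rate of 40%. An arm closes at 9 or more severe toxicities in the first 24 patients, and is rejected at 18 or more in 54.

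Other sections bear on what the count should contain:

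- Section 12.1: "Hematological toxicity is common but not too relevant for this study", and "All patients developed lymphopenia". No grade is given for the lymphopenia and no grade 4 haematological rate is stated.
- Section 10: the only toxicity reason for going off treatment is excessive extra-medullary toxicity.
- Section 13.1: an adverse event can be "any unfavorable and unintended sign (including an abnormal laboratory finding), symptom, or disease temporally associated with the use" of the product.
- Section 13.2: adverse events of grade 2 or higher go on the CRF; only disease progression is excepted.

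**The concern.** The endpoint and the safety background disagree about scope. Section 12.1 sets haematological toxicity aside, while sections 17.1 and 17.2 as worded count it at grade 4. Laboratory findings can be adverse events, and eligibility (8.1.1 and 8.1.2) sets no minimum blood count, so patients may enter already cytopenic from their leukaemia. The term side effect is not defined. The causality scale in section 13.2 is written for serious adverse events, and nothing says how drug-related cytopenia is told apart from cytopenia of relapsed ALL.

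An arm that crosses the limit is declared unsuitable for further investigation. If blood counts enter the tally, that conclusion can be reached with infections and organ toxicity at a level the design calls acceptable. The limits of 20% and 40% have a meaning only for a defined event.

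**Working it through.** **Inputs (section 17.1).** n1 = 24 and n = 54 per arm. Continue with at least 6 CRs and at most 8 severe toxicities in 24. Accept with at least 15 CRs and at most 17 severe toxicities in 54. CR rates 20% and 40%; toxicity rates 40% (unacceptable) and 20% (acceptable); both alphas and beta 0.10. CR and toxicity are taken as independent, and toxicity is counted as patients affected.

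**Formulas.** With b(n, x, p) the binomial probability and Y ~ Bin(30, p):

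- Pass on CR: C(p) = Σ over x = 6 to 24 of b(24, x, p) · P(Y ≥ 15 − x)
- Pass on toxicity: T(p) = Σ over x = 0 to 8 of b(24, x, p) · P(Y ≤ 17 − x)
- First-stage toxicity stop: S(p) = P(Bin(24, p) ≥ 9)

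**The plan's own design.** C(0.2) = 0.0881, C(0.4) = 0.9470, T(0.4) = 0.1015, T(0.2) = 0.9557. Hence:

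- alpha for CR = 0.0881 × 0.9557 = 0.084
- alpha for toxicity = 0.9470 × 0.1015 = 0.096
- power = 0.9470 × 0.9557 = 0.905

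All three meet the stated limits. A grid search (n 40–59, n1 14–35) returns 24/54 with these cut-offs as the optimum. The stated intervals, 15.0–39.7% for 14/54 and 21.1–47.5% for 18/54, also reproduce. The sample size arithmetic is sound.

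**Adding haematological grade 4.** Assumption: other grade 4 toxicity is 20%, and haematological grade 4 occurs independently in a proportion h of patients. The total is p = 1 − 0.8 × (1 − h); for example, h = 10% gives 1 − 0.8 × 0.9 = 28%. Power is C(0.4) × T(p). The last column is S(p) squared, for equal rates and independent arms, leaving aside the rule that averages the arms.

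| h | Total p | First-stage stop S(p) | Rejected for toxicity, 1 − T(p) | Power | Both arms stop at stage 1 |
|---|---|---|---|---|---|
| 0 | 20% | 0.036 | 0.044 | 0.905 | 0.001 |
| 10% | 28% | 0.206 | 0.315 | 0.649 | 0.042 |
| 25% | 40% | 0.672 | 0.898 | 0.096 | 0.452 |
| 37.5% | 50% | 0.924 | 0.996 | 0.003 | 0.854 |
| 50% | 60% | 0.992 | 1.000 | 0.000 | 0.985 |

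**Sensitivity to independence.** If haematological grade 4 fell only in patients who already had another grade 4 event, h = 10% would leave the total at 20% and change nothing. If h = 25% included all of those patients, the total would be 25%: stop 0.121, power 0.782. With no overlap, h = 10% gives 30%: stop 0.275, power 0.543.

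**Averaging rule.** Section 17.1 uses the mean of the two arms' toxicity rates when arm B is below arm A. High rates in both arms average to a high rate, so this gives no protection.

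**The case against.** The best defence is that side effect was never meant to cover blood counts. Section 5.4 lists the antibody's side effects without any blood count, and then names lymphocyte depletion separately as the cause of opportunistic infection; the pairing of side effect with infection in 17.1 could mirror that. Section 13.1 speaks of unintended signs, and lymphocyte depletion is arguably intended. Sections 12.1 and 10 point the same way. This reading is possible, and it suggests loose wording rather than a deliberate choice. But no section defines the term so, and the literal text governs a primary endpoint and a closure rule. The interim questionnaire and CRF instructions are not shown and may contain a counting rule. Differences between sites are therefore not established, but the conflict inside the protocol remains.

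Two stronger readings are tempting and are not supported:

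- A reader might infer that the rule is bound to close both arms, since every earlier patient had lymphopenia. Section 12.1 gives no grade for it. At a total rate of 30%, an arm stops at stage 1 with probability 0.275; near-certain closure of both arms needs about 60%.
- A reader might infer that every blood and marrow grade should leave the count. Section 5.4 says CD52 was not found on bone marrow stem cells and that treatment should not compromise normal haematopoiesis. Severe drug-related marrow suppression could therefore be a real safety signal, and a blanket exclusion would hide it from the rule.

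**Conclusion.** The concern holds in conditional form. The severe-toxicity definition in 17.1 and 17.2 conflicts with 12.1 and section 10. Taken literally, it lets expected lymphocyte depletion or leukaemic cytopenia count towards closing an arm.

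The protocol supplies no grade 4 haematological rate, so only a range can be given. Under independence, with other grade 4 toxicity at 20%, a 10% haematological rate already lowers power from 0.905 to 0.65. A 25% rate brings an arm with acceptable other toxicity to the design's unacceptable 40%, with power 0.10. Closure of both arms at the first stage becomes likely (0.85) only at a total of 50%. Power throughout supposes a true CR rate of 40%. The fault lies in what is counted; the cut-offs and patient numbers are correct for a properly defined event.

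**What to change.** Bring 14.1, 17.1, 17.2 and the interim questionnaire into line with 12.1 and section 10:

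- Restrict the event counted against the 20% and 40% limits, so that expected lymphopenia and cytopenia attributable to active leukaemia do not count. Say how attribution to leukaemia is judged; section 11.2 already collects haematology at entry.
- Have the sponsor state explicitly whether other drug-related marrow suppression of grade 4 counts. That is a clinical judgement which the documents leave open.
- Tabulate all haematological grade 4 events separately by arm, so that nothing is lost from the safety report.

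The cost is about one sentence in the definition, carried into the places that repeat it, and a matching item on the questionnaire. The 9/24 and 18/54 limits, the 20%/40% rates and the sample size stay as they are.

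### The 95% confidence intervals printed at the final decision limits in Protocol 17.1 ignore the interim stop and so appear to exclude the 40% CR and 20% toxicity targets; exact two-stage intervals include both

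*Protocol*

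**What the plan says.** Protocol 17.1 applies a Bryant-Day two-stage design to each arm: "in each treatment arm a maximum of 54 patients who started with induction cycle I will be assessed after induction cycle I". The interim analysis comes after 24 patients. The arm closes "if after the first 24 patients in a treatment arm ≤ 5 CR's (20.8%) are observed", "or if ≥ 9 severe toxicities (37.5%) are observed". An arm that continues is rejected at 54 patients with 14 or fewer CRs, printed as "14/54 = 25.9%, 95% CI = 15.0-39.7"%, or with 18 or more severe toxicities, printed as "18/54 = 33.3%, 95% CI = 21.1-47.5"%.

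The same section sets the uninteresting CR rate ("In the present trial, P_{CR0} has been taken as 20"%) and the CR target ("In the present trial, P_{CR1} has been taken as 40"%). The unacceptable and acceptable severe toxicity rates are 40% and 20%. Both alphas and beta are 0.10.

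Section 17.1 names no interval method and mentions no adjustment for the interim look. For the final report, 17.2 says: "The estimated CR rate after induction cycles 1 and 2 along with the 95% CI interval will be presented for each treatment arm". It plans the same for severe toxicity, again without naming a method.

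**The concern.** An arm reaches 54 patients only if its first 24 gave at least 6 CRs and at most 8 severe toxicities. An interval that treats 54 as fixed in advance leaves out the outcomes that end at stage 1. At the rejection limits this moves each bound in the direction that matters: the upper CR bound comes out too low and the lower toxicity bound too high.

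Both bounds fall just on the wrong side of a design target. The printed CR upper bound of 39.7% is below 40%, and the printed toxicity lower bound of 21.1% is above 20%. A reader would take an arm that fails by the narrowest margin to be incompatible, at the 95% level, with the rate that would justify further study. What is at stake is how a borderline rejection is read, not whether the arm is rejected.

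**Working it through.** **Inputs (all from Protocol 17.1).** Stage sizes are 24 and 54 − 24 = 30. Write X1 and Y1 for CRs and severe toxicities in the first 24, and X and Y for the totals at 54. Stage 1 closes the arm if X1 ≤ 5 or Y1 ≥ 9. The final analysis rejects if X ≤ 14 or Y ≥ 18. The targets are CR 40% and toxicity 20%.

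**Step 1: reproduce the printed intervals.** Clopper-Pearson for x of n takes the lower bound as the 2.5% point of Beta(x, n − x + 1) and the upper bound as the 97.5% point of Beta(x + 1, n − x). With n = 54:

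| Count | Printed | Clopper-Pearson | Wald | Wilson |
|---|---|---|---|---|
| 14/54 | 15.0-39.7% | 14.96-39.65% | 14.2-37.6% | 16.1-38.9% |
| 18/54 | 21.1-47.5% | 21.09-47.47% | 20.8-45.9% | 22.2-46.6% |

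Of these methods only fixed-sample Clopper-Pearson matches.

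**Step 2: tail probabilities at the targets.** The two-stage tail for a result at the limit or worse includes the stage-1 stop.

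- CR at 40%: P(X1 ≤ 5) + P(X1 ≥ 6 and X ≤ 14) = 0.040 + 0.013 = 0.053. The fixed-sample tail P(X ≤ 14) is 0.022.
- Toxicity at 20%: P(Y1 ≥ 9) + P(Y1 ≤ 8 and Y ≥ 18) = 0.036 + 0.008 = 0.044. The fixed-sample tail P(Y ≥ 18) is 0.015.

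Both fixed-sample tails are below 0.025 and both two-stage tails are above it. Under the stated design neither target is excluded at the two-sided 95% level.

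**Step 3: cross-check with the design's own errors.** These two-stage tails are the probabilities of rejecting a regimen that is exactly on target. The CR rule passes an arm at 40% with probability 0.947, and 1 − 0.947 = 0.053. The toxicity rule passes an arm at 20% with probability 0.956, and 1 − 0.956 = 0.044. With the endpoints independent, power is 0.947 × 0.956 = 0.905, so beta is 0.095, within the planned 0.10. The other errors also hold to the plan: alpha for CR is 0.084 (toxicity at 20%) and alpha for toxicity is 0.096 (CR at 40%). The design is sound; the printed intervals do not reflect it.

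**Step 4: exact two-stage intervals.** Put 2.5% in each tail and solve for p.

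- CR 14/54, lower bound: P(X1 ≥ 6 and X ≥ 14) = 0.025 gives 15.6%. Upper bound: P(X1 ≤ 5) + P(X1 ≥ 6 and X ≤ 14) = 0.025 gives 43.0%.
- Toxicity 18/54, lower bound: P(Y1 ≥ 9) + P(Y1 ≤ 8 and Y ≥ 18) = 0.025 gives 18.4%. Upper bound: P(Y1 ≤ 8 and Y ≤ 18) = 0.025 gives 46.4%.

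| Limit | Printed | Exact two-stage | Target | Target inside two-stage interval? |
|---|---|---|---|---|
| CR 14/54 | 15.0-39.7% | 15.6-43.0% | 40% | yes |
| Toxicity 18/54 | 21.1-47.5% | 18.4-46.4% | 20% | yes |

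Ordering outcomes by stage or by the observed proportion gives the same intervals at these two limits.

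**Step 5: how far the effect reaches.** Take the ordinary interval with n = 24 if stopped and n = 54 otherwise. Over a half-point grid of true rates its lowest two-sided coverage is about 94.5% for CR and 94.8% for toxicity. At the targets it is 95.9% (CR 40%) and 96.9% (toxicity 20%). For a clearly passing arm with 20/54 CRs the ordinary interval is 24.3-51.3% and the two-stage interval 24.3-51.4%.

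**The case against.** The strongest objection is that nothing is decided by these intervals. The rules in 17.1 are counts, the intervals stand in parentheses, and the text never claims that 40% or 20% is excluded. This stands, and it limits the point to interpretation. A reader might infer that the thresholds, error rates or sample size are wrong; Step 3 shows they are not.

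A second tempting inference is that ordinary exact intervals fail in this design generally, so that every final estimate is compromised. The coverage figures do not support that, and for clearly passing arms the difference all but vanishes.

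Third, 17.2 names no method, and a choice of method may properly sit in a statistical analysis plan that is not shown. That is fair: the silence of 17.2 is not a fault. The point rests on two figures that 17.1 prints. The sentence proposed for 17.2 only keeps the final report in line with them.

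Fourth, the replacement figures also simplify. An arm closes on either endpoint, the interim may be triggered early by the ninth toxicity, up to 4 more patients per arm may be randomized before the hold, and the A/B averaging rule can replace an arm's own rates. None of this is in the calculation. This stands too, so the new figures must carry a label saying what they assume. They are still closer to the stated design than intervals with no interim stop.

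Finally, a reader might suppose that for any arm closed at 24 the two-stage and ordinary exact intervals coincide. They do so only for the endpoint that itself triggered the stop, with all 24 assessed. An arm closed for toxicity may have 6 or more CRs: if both true rates are 40% and the endpoints independent, 64.5% of arms stop at 24 for toxicity with at least 6 CRs. The CR-only calculation has no such stopping outcome.

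**Conclusion.** The point holds as one about two stated figures. The intervals printed at the final limits are fixed-sample intervals in a design that is not fixed-sample, and they place both targets just outside. With the interim stop included, the CR upper bound moves from 39.7% to 43.0% and the toxicity lower bound from 21.1% to 18.4%, and both targets fall inside. A result at the limit or worse has probability 0.053 at the CR target and 0.044 at the toxicity target.

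The weight is modest: only the reading of arms near a rejection limit is affected. The figures assume that each endpoint is taken with its own stage-1 stop alone, that exactly 24 and then 30 patients are assessed, and that the A/B averaging rule is not applied.

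**What to change.** 1. In 17.1, replace the two intervals with 15.6-43.0% for 14/54 CRs and 18.4-46.4% for 18/54 severe toxicities. Label them as exact two-stage intervals computed per endpoint with its own interim stop.
2. In 17.2, state that for an arm completing stage 2 the cycle I CR rate and the severe toxicity rate are reported with exact two-stage (stage-wise ordering) 95% intervals.
3. For an endpoint that did not trigger closure, or an arm closed with fewer or more than 24 assessed patients, report the ordinary exact interval and label it as fixed-sample.

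The cost is two figures, a few sentences and a few lines of code. No extra patients or data are needed, and no decision rule changes. Near the limits the intervals will support a less firm statement than the printed ones suggest.

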13.3 Processing of serious adverse event reports

The HOVON Data Center will forward all reports within 24 hours of receipt to the study coordinator and the study central data manager. The report of an SAE will be the signal for the central data manager to ask the investigator or the responsible local data manager to complete

and send as soon as possible all relevant CRF's for the involved patient with details of treatment and outcome.

14 Endpoints

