17.4 Data and safety monitoring board

A data and safety monitoring board will not be installed.

18 Ethics

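### The early toxicity trigger (9 severe toxicities) is not linked to the 24-hour SAE reports; if counted only from the end-of-cycle questionnaire it can fire about 3 to 6 weeks late

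*Protocol*

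**What the plan says.** - **Trigger.** Protocol 17.1 plans an interim analysis in each arm after 24 patients, "or as soon as 9 severe toxicities have been reported in the first 24 registered patients, whichever comes first". The closing rule reads: "if after the first 24 patients in a treatment arm ≤ 5 CR's (20.8%) are observed, or if ≥ 9 severe toxicities (37.5%) are observed". Severe toxicity is any CTCAE grade 4 side effect or infection during induction cycle I.
- **Data tool.** The last paragraph of 17.1 has CR and toxicity data on cycle I requested monthly before the interim. For this, "a short questionnaire will be generated, which should be completed as soon as cycle I has been evaluated", or once it is decided that cycle I will not be given.
- **Cycle length.** In 9.2, alemtuzumab runs from day 8 to day 44, with evaluation at most two weeks after the last dose (about day 58).
- **SAE route.** Section 13.2 requires SAEs to reach the data center by fax within 24 hours of observation. Under 13.3 the data center must "forward all reports within 24 hours of receipt to the study coordinator and the study central data manager", and each report prompts the central data manager to ask for that patient's case report forms as soon as possible.
- **Holds and oversight.** Section 17.1 states a hold on randomisation only once 24 patients plus at most 4 more have been randomised per arm. Section 17.4 states: "A data and safety monitoring board will not be installed".

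**The concern.** The early trigger serves its purpose only if severe toxicities are counted close to when they happen. The tool named for the count reports at the end of a cycle that lasts more than five weeks from first to last infusion. The faster route exists, but nothing ties it to the count. A grade 4 event that does not meet the SAE definition has no stated immediate route at all, because SAE status in 13.1 depends on outcome and not on grade.

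The stake is patient exposure. Between the ninth severe toxicity and the moment someone counts it, patients continue to be randomised to an arm that has reached its own stopping number. No monitoring board watches in between, and no pause is stated for the interval between the ninth report and the interim result.

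**Working it through.** **1. The plan's own design reproduces.** Exact two-stage binomial calculation, CR and toxicity taken as independent, n1 = 24, n = 54, cut-offs 5/14 (CR) and 9/18 (toxicity):

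- P(pass CR): 0.0881 at a true CR rate of 20%, 0.9470 at 40%.
- P(pass toxicity): 0.1015 at a true toxicity rate of 40%, 0.9557 at 20%.
- α_CR = 0.0881 × 0.9557 = 0.084; α_tox = 0.9470 × 0.1015 = 0.096; power = 0.9470 × 0.9557 = 0.905.

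All meet the stated limits of 0.10. The data route does not enter these figures.

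**2. How often the trigger matters.** P(at least 9 of 24) is 0.04 at a true toxicity rate of 20%, 0.67 at 40% (the protocol's unacceptable rate), 0.92 at 50% and 0.99 at 60%.

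**3. Lag if only the questionnaire is counted.**

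- Single example: an event on day 12 is recorded on day 44 to 58, which is 44 − 12 = 32 to 58 − 12 = 46 days later.
- On average, assuming onset uniform over days 8 to 44 (mean 26) and the form uniform over days 44 to 58 (mean 51): 51 − 26 = 25 days. An assumed wait of 0 to 30 days for the monthly request (mean 15) makes it 40 days.
- Other assumptions, against a count made one day after onset: a form on day 45 gives a median delay of about 18 days, on day 58 about 30 days, and on day 58 in monthly batches about 35 to 46 days.

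**4. Patients entered during the lag.** Accrual is 60 per year over two arms, so 30 per year per arm. Extra patients ≈ lag × 30/365.25: 18 days gives 1.5, 25 gives 2.1, 40 gives 3.3 and 46 gives 3.8, before the cap of 28.

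**5. Simulation of one arm.** 20,000 runs, Poisson accrual of 30 per year, first 24 patients counted, cap 28. Mean number entered when the ninth toxicity is known, among runs that reach nine:

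| Source of the count | 40% toxic | 50% | 60% | 70% |
|---|---|---|---|---|
| Every event, one day after onset | 21.5 | 19.5 | 17.1 | 15.1 |
| 75% by SAE report, rest by form on day 58 | 22.1 | 20.1 | 17.8 | 15.7 |
| 50% by SAE report, rest by form on day 58 | 22.7 | 20.7 | 18.4 | 16.3 |
| Form only, day 45 | 22.9 | 20.9 | 18.6 | not run |
| Form only, day 58 | 23.8 | 21.9 | 19.7 | 17.6 |
| Form only, day 58, monthly batches | 24.7 | 23.0 | 20.9 | 18.9 |

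Excess over the first row, from unrounded means: 1.3 to 1.5 (day 45), 2.3 to 2.6 (day 58), 3.2 to 3.8 (monthly batches), 1.2 to 1.3 (50% by SAE report), about 0.6 (75%).

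**6. Sensitivity to the SAE share**, with the form uniform over days 44 to 58 and 50% true toxicity. Extra patients per arm without/with the monthly wait: 2.0/3.1 at a 0% share, 1.0/1.6 at 50%, 0.6/0.9 at 75%, 0.3/0.4 at 90%. At 75% the mean lag is about 7 to 11 days.

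**The case against.** A reader might infer that the two paragraphs of 17.1 contradict each other outright, that the trigger is bound to fire weeks late, and that 2 to 3 extra patients per arm is the expected cost. The document does not support that reading:

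- The trigger depends on toxicities having been reported, and no channel is excluded. The questionnaire is the only tool named, but it is not called the only source.
- Many grade 4 infections are likely to meet the SAE definition (life-threatening, or hospitalisation). The data center would then hold the report within a day, and 13.3 makes it the signal for prompt collection of forms. A delay of 32 to 46 days for such an event assumes that a report already in hand is not counted.
- The figure of 2 to 3 patients assumes that no event is counted from an SAE report. That is one end of the range.
- Patients who progress, cannot reach the study dose or stop for toxicity leave cycle I early, so their forms may come sooner. In the other direction, 9.4 allows an interruption of up to 21 days, which can push the form past day 58.
- The closing rule already shuts an arm at 9 or more severe toxicities, and entry before the interim result cannot exceed 28.

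Most of this stands, and it limits the size of the problem. It does not supply the missing link: no sentence makes an SAE report count toward the 9, grade 4 events that are not SAEs may appear only on the end-of-cycle form, and no pause is stated between the ninth report and the interim result.

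**Conclusion.** The point holds as a gap in how the trigger is operated. The protocol asks for a prompt interim analysis at the ninth severe toxicity, names a slow tool to feed it, and leaves the fast route unconnected.

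If only the questionnaire is counted, the trigger can fire about 3 to 6 weeks late, with roughly 1 to 4 more patients entering the arm. If part of the grade 4 events is counted from SAE reports, the excess is about 1 to 1.6 patients at a 50% share and 0.6 to 0.9 at 75%, and it approaches zero as the share nears 100%.

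These sizes rest on assumptions the protocol does not supply: the SAE share, event onset, form dates, the wait for the monthly request, and steady accrual at the expected rate. The rule that averages toxicity over both arms when arm B's rate is below arm A's was not modelled. Type I errors, power and cut-offs do not change. The case for acting is patient protection at little cost.

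**What to change.** 1. **Sections 17.1 and 13.3:** state that each patient's first CTCAE grade 4 event in cycle I counts toward the 9 when it arrives as an SAE report. The central data manager keeps the count for each arm and makes sure the grade is captured. The SAE form is not shown, so it may already record it.
2. **Section 17.1:** keep the questionnaire for CR, for grade 4 events that are not SAEs, and for reconciling the running count.
3. **Section 17.1, stopping rules:** when the ninth severe toxicity in an arm is reported, pause randomisation to that arm until the interim analysis, including the arm-averaging rule, has been applied. It should be a pause and not a closure, because under the averaging rule nine events in one arm need not close it.

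**Cost:** some protocol wording and slightly more data management work. Randomisation may be paused briefly for an event that is later downgraded, or for an arm that averaging then keeps open. Grade 4 events that are not SAEs would still be counted late. Closing that remainder would need a new duty to report them at once, which is not proposed here.
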